12.2.3 Planned Subgroup Analyses

Subgroup analyses will be carried out in order to investigate immune responses in disease-specific cohorts. Comparisons of vaccine performance within specific diseases will be examined.

12.2.4 Exploratory Analyses

A descriptive analysis of the reported adverse events in the participants will be presented.

The exploratory analyses will utilise the methods to analyse data as described in Section 12.2.2 where appropriate.

12.2.5 Interim Analyses

An interim analysis will be undertaken on the first 160 patients (combining all disease groups, including participants in the main randomisation and sub-study randomisation). This will be a descriptive analysis of the magnitude of the anti-spike and anti-nucleocapsid Ig response, the Menarini Diagnostics surrogate neutralisation antibody response and the T cell responses as measured by the Oxford Immunotec modified T-SPOT Discovery SARS-CoV-2 assay. A further interim analysis will be conducted as the results may be relevant to the public's interest. The analysis will be conducted as specified in the SAP.

12.2.6 Sample Size Justification

12.2.6.1 Primary outcome sample size justification

A power calculation based on a paired T-Test was performed using Stata version 17.0 (Stata Corps, USA) to estimate the detectable effect size based on a proposed recruitment of 1100 participants (this reduction of 60 participants allows for withdrawal or loss to follow-up). It was found that with 1100 pairs using 90% power and significance (alpha) set to 5%, a very small effect size of 0.0978 would be detectable. For 800 evaluable patients with a significance (alpha) set at 5% an effect size of 0.0978 would be detectable with 79% power.

12.2.6.2 Secondary outcome sample size justification for sub-study randomisation

There is a potential for 320 participants to be recruited to the sub-study, however, in order to allow for drop out or recruitment failures, a total number of 300 recruits has been used in the power calculation. A power calculation based on an ANOVA statistical test was carried out using Stata version 17.0 (Stata Corps, USA) to estimate the detectable effect size based on total sample size number of 300 participants, recruited into one of three treatment arms (Pfizer, Moderna or Novavax, n=100 in each arm). Using power of 80%, significance (alpha) set at 5%, an effect size of 0.1801 would be detected.

These power calculations will be revised should the recruitment numbers differ from those predicted.

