Immunocompromised Patients

- Aged ≥ 18 years
- Have a suboptimal response to two doses of SARS-CoV-2 vaccine
- Anticipated life expectancy of 6 months or greater
- One (or more) of the patient cohorts specified below, and meet disease relevant classification, disease state, and staging according to established international standards
- For the randomised sub-study only, female participants of childbearing potential must be willing to ensure that they or their partner use acceptable effective contraceptive methods

Main Study Randomisation

Sub-study Randomisation

† Note: lymphoid malignancy patients can be randomised to the Main Study randomised comparison only or the sub-study. Sub-study participants randomised to Pfizer and Moderna arms will be included in the Main Study randomised comparisons also

Key

CAR-T = chimeric antigen receptor (CAR)T cell; GI = Gastrointestinal disease; HSCT = Haematopoietic stem cell transplant; IM = Immune mediated; IST = Immune suppressive therapy; PID = Primary immunodeficiency

TABLE OF CONTENTS

1 BACKGROUND AND RATIONALE..... 1

1.1.1 OCTAVE-DUO Trial Hypotheses 3

2 AIM, OBJECTIVES AND OUTCOME MEASURES..... 3

2.1.1 Primary Objective 3

2.1.2 Secondary Objective 3

2.1.3 Exploratory Objective 4

2.2 Outcome Measures 4

2.2.1 Primary Outcome 4

2.2.2 Secondary Outcomes..... 4

2.2.3 Exploratory Outcomes..... 5

2.2.3.1 Safety..... 5

2.2.3.2 Cellular Immunogenicity 5

3 TRIAL DESIGN AND RECRUITMENT TARGETS..... 5

3.1 Trial Design..... 5

3.2 Recruitment Targets 6

3.2.1 Anticipated Recruitment by Disease Cohort 6

4 ELIGIBILITY 7

4.1 Inclusion Criteria..... 7

4.2 Exclusion Criteria 10

5 SCREENING AND CONSENT 10

5.1 Screening..... 10

5.2 Informed Consent..... 11

6 TRIAL ENTRY..... 12

6.1 Randomisation 12

6.1.1 Main Study Randomisation 13

6.1.2 Sub-study Randomisation..... 13

6.1.3 Following Randomisation 14

7 TRIAL TREATMENT..... 14

7.1 Investigational Medicinal Products..... 14

7.1.1 Pfizer SARS-CoV-2 Vaccine..... 15

7.1.2 Moderna SARS-CoV-2 Vaccine..... 15

7.1.3 Novavax COVID-19 Vaccine 15

7.2 Administration of Investigational Medicinal Products 17

7.2.1 Pfizer SARS-CoV-2 Vaccine..... 17

7.2.2 Moderna SARS-CoV-2 Vaccine 17

7.2.3 Novavax SARS-CoV-2 Vaccine 17

7.3 Assessments 17

7.3.1 Screening 17

7.3.2 Baseline 18

7.3.3 Re-Boost vaccination 18

7.3.4 Post Re-boost vaccination 19

7.3.5 Three Month Follow-up..... 19

7.4 Contraception and Pregnancy for Participants in Randomised Sub-study 20

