3.2 Recruitment Targets

Up to 1200 participants will be recruited from the 8 different disease cohorts. The numbers recruited per cohort will vary as indicated below.

Initiation of recruitment into each cohort will be staggered with lymphoid malignancy, immune-mediated rheumatic diseases, end stage kidney, chronic liver disease, and gastrointestinal disease on immunosuppressive therapy and patients being prioritised in the initial recruitment phase of the trial.

The target recruitment for the study components (see Section 12.2.6 for power calculations) are:

- Main study - minimum of 1100 participants will contribute to the analysis
- Randomised sub-study – minimum of 300 participants will contribute to the analysis

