3.2.1.2 Lymphoid Malignancies

Target 320 participants. Target recruitment per disease cohort sub-type:

- Aggressive B-Non Hodgkin Lymphoma (NHL) - 40 participants
- Chronic lymphocytic leukaemia (CLL) - 80 participants
- Hodgkin Lymphoma - 40 participants
- Indolent B NHL (except CLL and small lymphocytic lymphoma (SLL)) - 80 participants
- Myeloma - 80 participants

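### The sub-study's 300 analysed participants and 80% power rest on a pool that is the whole lymphoid cohort, although lymphoid patients may enter the main study only and the protocol's totals imply a smaller sub-study

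*Protocol*

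**What the plan says.** - **Size of the lymphoid cohort.** Protocol Section 3.2.1.2: "Target 320 participants. Target recruitment per disease cohort sub-type". The five sub-types are 40, 80, 40, 80 and 80, which sum to 320.
- **Size of the sub-study.** Section 12.2.6.2: "There is a potential for 320 participants to be recruited to the sub-study". To go from 320 to the number used, it says "in order to allow for drop out or recruitment failures", "a total number of 300 recruits has been used in the power calculation". The arms are "Pfizer, Moderna or Novavax, n=100 in each arm", and the result is "Using power of 80%, significance (alpha) set at 5%, an effect size of 0.1801 would be detected". The section closes by saying that the calculations will be revised if recruitment turns out differently.
- **Target for analysis.** Section 3.2, for the randomised sub-study: "minimum of 300 participants will contribute to the analysis". The same list sets a minimum of 1100 for the main study, from a total of up to 1200.
- **Who enters the sub-study.** The note to the trial design figure: "lymphoid malignancy patients can be randomised to the Main Study randomised comparison only or the sub-study". It adds that sub-study patients on Pfizer or Moderna also count in the main comparison. No expected share, cap or rule for main-only entry is given.
- **Combined mRNA arms.** Section 12.2.1 bases the primary analysis on 1160 participants recruited to Pfizer and Moderna together. Section 6.1.2 allocates the sub-study 1:1:1.

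**The concern.** The pool for the sub-study calculation is the same 320 that Section 3.2.1.2 sets for all lymphoid patients. If some of them may be randomised between Pfizer and Moderna only, the sub-study cannot be assumed to receive all 320. The 20-patient allowance does not name that route. Section 3.2 nevertheless fixes at least 300 analysed, with the 80% power attached to that number.

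The sub-study is the only randomised comparison that includes Novavax. If enrolment falls well short of 300, a null three-arm result could be read against a stated 80% power that it did not have. The figure in Section 12.2.1 sharpens the question, because it appears to assume far fewer Novavax patients than Section 12.2.6.2 does.

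**Working it through.** **1. Reproduce the plan's figure.** One-way ANOVA with k = 3 arms, two-sided alpha not applicable (F test at 5%), effect size f, total N. Noncentrality is λ = N·f², and power = P[F′(2, N−3; λ) > F₀.₉₅(2, N−3)]. With N = 300 and f = 0.1801, λ = 300 × 0.1801² = 9.73 and power = 0.7999. Solving for 80% power at N = 300 returns f = 0.1801. The stated figure is reproduced.

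**2. The margin.** 320 − 300 = 20, and 20/320 = 6.25%. This has to cover every reason for not being analysed in the sub-study: main-only entry, recruitment shortfall and drop-out.

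**3. How far the margin goes (illustration).** Section 12.2.6 gives no separate drop-out rate for the sub-study. Borrowing the loss in the primary calculation, 60/1160 = 5.2%, the entry needed for 300 evaluable is 300 / (1 − 60/1160) = 316.4, so 317 of 320. About 3 lymphoid patients could then be main-only. With no drop-out and no recruitment shortfall, the number would be 20.

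**4. Consistency with the trial totals.** The nine cohort targets in Section 3.2.1 are 80 + 320 + 160 + 160 + 80 + 80 + 80 + 160 + 80 = 1200.
- With 1160 on Pfizer plus Moderna, 1200 − 1160 = 40 remain for Novavax. At 1:1:1 the sub-study is 3 × 40 = 120, which would leave 320 − 120 = 200 lymphoid patients main-only.
- Conversely, a sub-study of 300 puts 100 on Novavax and leaves 1200 − 100 = 1100 on Pfizer plus Moderna. A sub-study of 320 leaves about 1093. Neither is 1160.
- The two minimums in Section 3.2 together need 1100 analysed on Pfizer or Moderna plus 100 analysed on Novavax. That is 1200 analysed from at most 1200 recruited, with no attrition at all.

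**5. Power over a range of evaluable N**, by the formula in step 1:

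| Evaluable N | Removed from 320 | Power at 0.1801 | Effect detectable with 80% power |
|---|---|---|---|
| 300 | 20 (6.25%) | 80% | 0.180 |
| 270 | 50 (15.6%) | 75% | 0.190 |
| 240 | 80 (25%) | 70% | 0.202 |
| 200 | 120 (37.5%) | 61% | 0.221 |
| 120 | 200 (62.5%) | 40% | 0.287 |

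The protocol does not state a main-only share, so the rows are a range and not a forecast. Only the last is implied by a figure in the protocol (1160 of 1200), and it assumes that 1200 are recruited and that 1:1:1 allocation holds.

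**The case against.** The strongest case on the other side has five parts.

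- **320 is worded as a potential, that is, a ceiling.** True. The protocol does not say that all 320 will enter. But Section 3.2 then fixes a minimum only 20 below that ceiling, so the ceiling reading does not free the number.
- **Recruitment failure can include a lymphoid patient who goes main-only.** This is a fair reading, and it is why step 2 counts all reasons together. The allowance is still 20 in total.
- **Section 12.2.6.2 promises revision.** It does, and this reduces the risk of misreading. It does not reconcile figures that already disagree in the current text, and it offers no alternative sizes. Section 12.2.6.1 does give one for the primary analysis (800 evaluable).
- **The 5.2% loss comes from another calculation.** Correct. The 317 is an illustration only; the limit of 20 does not depend on it.
- **Power falls slowly.** At N = 288 (10% of 320 lost) it is still 78%, a small shortfall for a secondary comparison.

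A reader might go further and infer that the power calculation is wrong, or that the sub-study will have only 50 to 70% power. The documents support neither: 0.1801 is correct for N = 300, and main-only shares of 20 to 50% have no source in the protocol. Nor does the wording in the objectives about a subset with lymphoid malignancies prove that only part of the cohort was meant, since it can equally describe lymphoid patients as a subset of the trial. The sub-study's extra conditions on contraception, pregnancy and lactation could divert some patients to the main study, but the protocol gives no number. The design figure is not shown in the text available, so any split printed in it could not be checked.

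**Conclusion.** The concern holds as a point about an unsupported and unreconciled sample size, not as an error in the ANOVA calculation. Reaching 300 analysed from a pool of 320 tolerates the loss of 20 patients (6.25%) for all reasons, while the design leaves main-only entry open without limit. Separately, 1160 on Pfizer plus Moderna out of 1200 is incompatible with a sub-study of 300 or 320 under equal allocation; it implies about 120, and 40% power at 0.1801. The protocol therefore carries sub-study sizes from about 120 to 320 without saying which one is planned.

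What rests on assumption: full recruitment to 1200 and 1:1:1 allocation for the figure of 120, and the borrowed 60/1160 loss for the figure of 317. The true main-only share is unknown, so the actual loss of power cannot be estimated from the protocol; it is small if few patients go main-only and substantial if a quarter or more do.

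**What to change.** In Sections 3.2 and 12.2.6.2:

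1. State the expected number of lymphoid patients in the sub-study and in the main study only.
2. Reconcile that split with the 1160 in Section 12.2.1, the 1100 in Section 3.2 and the total of 1200.
3. Replace the minimum of 300 with the number that the design supports after main-only entry and attrition.
4. Report power at 0.1801 and the effect detectable with 80% power for a range of evaluable numbers, such as the 300, 270, 240, 200 and 120 tabulated above.

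The cost is wording only. No extra patients are needed, but the stated sub-study power becomes less favourable. Requiring every lymphoid patient who meets the sub-study criteria to enter it would also bring the pool closer to 320, but it removes an option that the design deliberately offers. It is a trade-off for the trial team and not the main remedy.

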13 TRIAL ORGANISATIONAL STRUCTURE

This is a collaborative trial being conducted by the University of Glasgow, University of Birmingham, University of Oxford and Imperial College London. Additional sites will participate in the study.

13.1 Sponsor

The trial is being sponsored by the University of Birmingham.

13.2 Coordinating Centre

The trial is being conducted under the auspices of the CRCTU, University of Birmingham according to their local procedures.

13.3 Access Committee

An Access Committee has been established to ensure the appropriate governance of the research samples. Samples will be made available to academic researchers for ethically approved studies, subject to the approval of the Access Committee.

13.4 Trial Management Group

The Chief Investigator, Deputy Chief Investigator, cohort leads, co-investigators, trial statisticians, Patient and Public Involvement and Engagement (PPIE) representatives, Trial Management Team Leader and Trial Coordinator will form the TMG. The TMG will be responsible for the day-to-day conduct of the trial. They will be responsible for the clinical set-up, promotion, ongoing management of the trial, the interpretation of the results and preparation and presentation of relevant publications.

The TMG will meet formally (virtually) weekly during the recruitment phase of the trial. Thereafter the formal TMG meetings may be replaced by a regular progress report.

The membership of the OCTAVE-DUO TMG is almost identical to the OCTAVE TMG hence it is anticipated joint meetings will be held whenever possible.

13.5 Trial Steering Committee

The TSC will be set up to oversee the trial. Membership will be composed of independent clinicians and at least one patient advocate. Members of the TMG will report to the TSC. The TSC will meet three monthly once the trial opens to recruitment, they will supervise the conduct of the trial, monitoring progress including recruitment, data completeness, losses to follow-up, and deviations from the protocol. They will make recommendations about conduct and continuation of the trial.

13.6 Data Monitoring Committee

Data analyses pertaining to trial conduct, data quality and patient safety will be supplied in confidence to an independent DMC, which will be asked to advise on whether the accumulated data from the trial, together with the results from other relevant research, justifies the continuing recruitment of further

patients. The DMC will operate in accordance with a trial specific charter based upon the template created by the Damocles Group. The DMC will meet following the interim analysis and then 3 monthly during recruitment. An emergency meeting may also be convened if a safety issue is identified. The DMC will report directly to the TSC. The DMC may consider recommending the discontinuation of the trial if the recruitment rate or data quality are unacceptable or if any issues are identified which may compromise patient safety.

13.7 Finance

This is an investigator-initiated and investigator-led trial funded by UK Research and Innovation (UKRI) in accordance with Medical Research Council grant terms and conditions. The trial has been adopted on to the NIHR CRN Portfolio.

Individual per patient payment will be made to NHS Trusts to cover the NHS Research costs.

Participants will be able to claim travel expenses for extra clinic visits but no other payments will be made for taking part in the trial.

Novavax SARS-CoV-2 vaccine is provided free of charge by the biotechnology company Novavax LTD.

Pfizer and Moderna SARS-CoV-2 vaccines will be supplied by PHE via the normal clinical supply route.

14 ETHICAL CONSIDERATIONS

The trial will be performed in accordance with the recommendations guiding physicians in biomedical research involving human subjects, adopted by the 18th World Medical Association General Assembly, Helsinki, Finland, June 1964, amended at the 48th World Medical Association General Assembly, Somerset West, Republic of South Africa, October 1996 (Appendix 5).

The trial will be conducted in accordance with the UK Policy Framework for Health and Social Care Research 2017, the applicable UK Statutory Instruments, which include the Medicines for Human Use Clinical Trials 2004 and subsequent amendments; the General Data Protection Regulation 2018; and Data Protection Act 2018; and Human Tissue Act 2004 or Human Tissue (Scotland) Act 2006 and GCP.

This trial will be carried out under a Clinical Trial Authorisation in accordance with the Medicines for Human Use Clinical Trials regulations. The protocol will be submitted to and approved by the REC and Health Research Authority prior to circulation.

Before any patients are enrolled into the trial, the Principal Investigator at each site is required to obtain formal confirmation of capacity and capability from their local R&D Department and provide evidence of this to the Trial Office. Sites will not be permitted to enrol patients until this has been obtained.

It is the responsibility of the Principal Investigator to ensure that all subsequent amendments gain the necessary local approval. This does not affect the individual clinicians' responsibility to take immediate action if thought necessary to protect the health and interest of individual patients.

15 CONFIDENTIALITY AND DATA PROTECTION

The University of Birmingham is the Data Controller for this trial. Personal data recorded on all documents will be regarded as strictly confidential and will be handled and stored in accordance with the General Data Protection Regulation 2018 and the Data Protection Act 2018. Data will be processed under Article 6 (i) (performance of a task carried out in the public interest) and Article 9 (j) (necessary for archiving purposes in the public interest, scientific or historical research purposes or statistical purposes in accordance with Article 89(1)). Information about how information is handled can be found in the CRCTU and University of Birmingham's privacy policies:

<https://www.birmingham.ac.uk/research/activity/mds/trials/crctu/crctu-privacy-notice.aspx>

The participant's initials, date of birth, NHS/CHI Number and hospital number will be collected at trial entry to aid in identification and matching with other data sources where appropriate for the purposes of further analysis. Patients will be identified using only their unique trial number and initials on the CRF and correspondence between the Trial Office and the participating site.

The investigator must maintain documents not for submission to the Trial Office in strict confidence. In the case of specific issues and/or queries from the regulatory authorities, it will be necessary to have access to the complete trial records, provided that participant confidentiality is protected.

Representatives of the CRCTU may be required to have access to patient's notes for quality assurance purposes but patients should be reassured that their confidentiality will be respected at all times.

The Trial Office will maintain the confidentiality of all participants' data and will not disclose information by which participant may be identified to any third party other than those directly involved in the treatment of the participant and organisations for which the participant has given consent for data transfer. Anonymised participant level data and research samples may be shared in accordance with the CRCTU Data Sharing Policy (see Section 18 for further details).

16 INSURANCE AND INDEMNITY

The University of Birmingham has in place indemnity which provides cover to the University for harm which comes about through the University's, or its staff's, negligence in relation to the design or management of the trial and may alternatively, and at the University's discretion provide cover for non-negligent harm to participants.

With respect to the conduct of the trial at site and other clinical care of the participant, responsibility remains with the NHS organisation responsible for the clinical site and is therefore indemnified through the NHS Litigation Authority.

The University of Birmingham is independent of any pharmaceutical company, and as such it is not covered by the Association of the British Pharmaceutical Industry (ABPI) guidelines for participant compensation.

17 PUBLICATION POLICY

Results of this trial will be submitted for publication in a peer reviewed journal. The manuscripts will be prepared by the TMG and authorship will be on behalf of the collaborative group in accordance with the trial Publication Policy.

Any secondary publications and presentations prepared by investigators must be reviewed by the TMG. Manuscripts must be submitted to the TMG in a timely fashion and in advance of being submitted for publication, to allow time for review and resolution of any outstanding issues. Authors must acknowledge that the trial was performed with the support of University of Birmingham and all funding bodies must be appropriately acknowledged in accordance with the funder's terms and conditions. Intellectual property rights will be addressed in the agreements between sponsor, collaborators and the sites.

The results of the trial will be made available on ISRCTN and provided to participants in the form of a lay summary on the trial website.

18 DATA SHARING

The CRCTU is committed to responsible and controlled sharing of anonymised clinical trial data with the wider research community to maximise potential patient benefit while protecting the privacy and confidentiality of trial participants. Data anonymised in compliance with the Information Commissioners Office requirements, using a procedure based on guidelines from the MRC Methodology Hubs, will be available for sharing with researchers outside of the trials team within 6 months of the primary publication.

More detailed information on the CRCTU's Data Sharing Policy and the mechanism for obtaining data can be found on the CRCTU website:

<https://www.birmingham.ac.uk/research/activity/mds/trials/crctu/index.aspx>.

